10. SUBJECT SAFETY MANAGEMENT/ STUDY STOPPING RULES

10.1 Study Stopping Rules

If any of these events occur, dosing will be placed on hold pending a full review of all available clinical safety data and discussion with the investigators and the DSMB.

- Two or more subjects receiving EDP-938 experience a similar Grade 3 study drug-related AE, including a confirmed treatment-emergent Grade 3 laboratory abnormality
- One or more subjects receiving EDP-938 experience a study drug-related SAE
- One or more subjects receiving EDP-938 experience Grade 4 or higher AE or a confirmed treatment-emergent laboratory abnormality regardless of causality attribution to study drug

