11.7.3 Clinical Laboratory Data

Laboratory assessments will be reported as mean change from Baseline across scheduled visits, and as the incidence rate of shift change from Baseline. Shift from Baseline tables will be generated for each treatment group for selected analytes. Laboratory shifts will be displayed as treatment-emergent abnormal, high, or low results. The following details the summary types where LLN = lower limit of normal and ULN = upper limit of normal.

For categorical tests: Treatment-emergent abnormal is defined as a change from normal at Baseline to abnormal at any post-Baseline visit.

For continuous tests:

- Treatment-emergent high is defined as a change from a result less than or equal to the high limit at Baseline to a value greater than the high limit at any time post-Baseline.
Results will be reported according to any value greater than the high limit, any value greater than $2 \times$ ULN and $3 \times$ ULN.
- Treatment-emergent low is defined as a change from a result greater than or equal to the low limit at Baseline to a value less than the low limit at any time post-Baseline.
Results will be reported to any value less than the lower limit, any value less than $2 \times$ LLN and $3 \times$ LLN.

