### 3.15.2 Clinical Laboratory Data

Laboratory assessments will be reported as the mean of observed and change from baseline across scheduled visits, and as the incidence rate of shift change from baseline. Shift from baseline tables will be generated for each treatment group for selected analytes. Laboratory shifts will be displayed as treatment-emergent abnormal, high, or low results. The following details the summary types where LLN = lower limit of normal and ULN = upper limit of normal.

For categorical tests: Treatment-emergent abnormal is defined as a change from normal at baseline to abnormal at any post-baseline visit.

For continuous tests:

- Treatment-emergent high is defined as a change from a result less than or equal to the high limit at baseline to a value greater than the high limit at any time post-baseline.

For all parameters except Glomerular Filtration Rate (GFR) results will be reported according to any value greater than the high limit, any value greater than  $2 \times$  ULN and  $3 \times$  ULN.

- Treatment-emergent low is defined as a change from a result greater than or equal to the low limit at baseline to a value less than the low limit at any time post-baseline.

Results for GFR will be reported according to any value less than  $(\frac{1}{2}) \times$  LLN and  $(\frac{1}{4}) \times$  LLN. All other results will be reported to any value less than the lower limit.

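### Except for GFR, the SAP tiers laboratory abnormalities only by multiples of ULN with a single low-side category, and it plans no table of laboratory values by toxicity grade

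*SAP*

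**What the plan says.** SAP 3.15.2 sets the high-side rule. For every parameter but GFR, "results will be reported according to any value greater than the high limit", followed by cut-offs at 2x and 3x ULN. On the low side, "Results for GFR will be reported according to any value less than" one half and one quarter of LLN, and then "All other results will be reported to any value less than the lower limit". The form of display is also fixed: "Laboratory shifts will be displayed as treatment-emergent abnormal, high, or low results". Its scope is not: "Shift from baseline tables will be generated for each treatment group for selected analytes", and those analytes are not named.

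Protocol 11.7.3 has a different low-side rule: "Results will be reported to any value less than the lower limit, any value less than" two and three times LLN. The SAP does not carry this over.

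Protocol 9.2 names NCI-CTCAE version 4.03 as the grading scale for adverse events. Among the events that put dosing on hold, Protocol 10.1 lists similar drug-related Grade 3 AEs in two or more EDP-938 subjects, "including a confirmed treatment-emergent Grade 3 laboratory abnormality". A further item there names a confirmed laboratory abnormality beside a Grade 4 or higher AE. SAP 3.15.1 plans tables of TEAEs of Grade 3 or higher and of TEAEs by maximum grade. SAP 3.15.2 has no counterpart for the laboratory values themselves.

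**The concern.** Multiples of ULN suit analytes that can rise severalfold, such as transaminases. Table 2 of the protocol also contains analytes held in a narrow band and analytes reported as percentages. For these a zero in the 2x or 3x row says little or nothing about safety, yet it may be read as reassurance.

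The low side is the larger gap. Falls are often what matters for haemoglobin, platelets, neutrophils, potassium and glucose, and the SAP counts a trivially low value and a critically low one in the same cell.

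Clinical laboratory results are a named safety endpoint. With about 35 subjects per arm, one or two marked abnormalities are worth showing as counts by arm. The protocol already expresses part of its safety oversight in laboratory grades, so a reader would expect the summary to use the same terms.

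**Working it through.** The plan states no figure to reproduce here. The check is a comparison of texts plus arithmetic on the cut-offs. The documents give no reference limits, so every ULN below is an assumption shown as a range, and haematocrit is assumed to be in percent.

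**1. When is a high-side row impossible?** A percentage cannot exceed 100, so the row above k x ULN must be empty once k x ULN >= 100, that is, once ULN >= 100/k. For k = 2 this is ULN >= 50%; for k = 3 it is ULN >= 33.3%.

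| Analyte | Assumed ULN (%) | 2x ULN (%) | 3x ULN (%) | Impossible rows |
|---|---|---|---|---|
| Neutrophils | 60-80 | 120-160 | 180-240 | 2x and 3x |
| Lymphocytes | 35-50 | 70-100 | 105-150 | 3x; 2x only at ULN = 50 |
| Haematocrit | 44-54 | 88-108 | 132-162 | 3x; 2x only if ULN >= 50 |
| Monocytes | 8-13 | 16-26 | 24-39 | none |
| Eosinophils | 4-8 | 8-16 | 12-24 | none |
| Basophils | 1-2 | 2-4 | 3-6 | none |

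**2. Rows that are possible in arithmetic but empty in practice.** These scales have no cap, so this step is a judgement of physiological plausibility.

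| Analyte | Assumed ULN | 2x ULN |
|---|---|---|
| Sodium, mmol/L | 144-148 | 288-296 |
| Chloride, mmol/L | 105-110 | 210-220 |
| Albumin, g/dL | 5.0-5.5 | 10-11 |
| Haemoglobin, g/dL | 15.5-18 | 31-36 |

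By contrast, for ALT with an assumed ULN of 35-55 U/L, 2x is 70-110 and 3x is 105-165 U/L. There the tiers do their job.

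**3. Low side in the SAP.** Take two subjects with normal baselines and post-baseline values of 0.95 x LLN and 0.20 x LLN. For any analyte but GFR, both add one to the same below-LLN count. For GFR, the first enters neither tier and the second enters both. GFR is not named in protocol Table 2, which lists estimated creatinine clearance, so the only low-side tiers may attach to a parameter that is not listed there.

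**4. Low side in the protocol.** For any positive LLN, a value below LLN is also below 2x and 3x LLN. Among treatment-emergent low values, all three rows in Protocol 11.7.3 would therefore hold the same subjects. Applied without that condition, the 2x and 3x rows would also take in values at or above LLN. Those tiers do not measure severity either, and the SAP supplied a working replacement only for GFR.

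**5. Can the AE tables stand in?** Under Protocol 8.4, a laboratory finding should be recorded as an AE if the Investigator considers it clinically significant. Protocol 9.1.2 and 9.2.1 tie it to symptoms, or to suspected latent symptoms. A value in the Grade 3 range that is not reported as an AE appears in no grade table planned in the SAP.

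**The case against.** The strongest reply is that little is hidden. SAP 3.1 requires minimum and maximum in quantitative summaries, and SAP 3.15.2 summarises observed values and changes by scheduled visit. A critically low platelet count at a planned visit would thus appear as that arm's minimum. All values are listed, and Protocol 11.7 has those outside the normal range flagged. This stands for single extremes. It does not give the number of subjects per arm with a marked abnormality.

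Three stronger readings are tempting, and the documents do not support them.

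- A reader might infer that the upper rows are impossible for many analytes. Strict impossibility reaches only the few percentage analytes in step 1; the rest is implausibility under assumed limits. The SAP does not call the 2x and 3x rows severe, and a zero in them would be a true statement. Because the analytes are unnamed and the table shells are in a separate document (SAP 3.1), it is not even certain that sodium or chloride would get such rows.
- A reader might infer that no table shows grades at all. SAP 3.15.1 plans two AE tables by grade, and laboratory abnormalities reported as AEs would be in them.
- A reader might infer that the hold rule cannot operate. It runs during the study, through review of all available safety data with the investigators and the DSMB, whose procedures are in a separate charter. It does not depend on the final tables.

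It is also fair to say that the protocol adopts NCI-CTCAE for adverse events and not expressly for laboratory values, and that its cut-offs are not reproduced in the documents. But no other grading scale is named, and Protocol 10.1 already speaks of a laboratory grade.

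**Conclusion.** The point holds as a minor reporting weakness. GFR apart, the SAP has one low-side category and a single set of ULN multiples whatever the analyte, and it plans no summary of laboratory values by toxicity grade. Three things rest on the text alone: the single low category, the missing grade summary, and the conflict with Protocol 11.7.3. The impossible rows (3x for neutrophil %, lymphocyte % and haematocrit; 2x for neutrophil %) and the practically empty ones rest on the assumed limits.

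The stake is small: about 70 subjects, laboratory tests on Days 1, 5 and 14, and descriptive safety analyses. Efficacy inference and the working of the hold rule are unaffected. The change is worth making because it turns uninformative cells into informative ones, using data already collected.

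**What to change.** In SAP 3.15.2:

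- For each Table 2 analyte that NCI-CTCAE v4.03 grades, tabulate worst post-baseline grade against baseline grade by arm, with high and low directions separate. Name the analytes. Which ones qualify, and at what cut-offs, must be taken from the scale itself.
- Keep the ULN multiples for liver and pancreatic enzymes, bilirubin and creatine kinase.
- Keep the out-of-range category for ungraded analytes.
- Reconcile the low-side tiers with Protocol 11.7.3, and state whether the GFR rule refers to the estimated creatinine clearance in Table 2.

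Parameter-specific criteria are already this SAP's practice for vital signs (3.15.3). The cost is SAP wording, grading code and one longer descriptive table. No sample, visit or clinical procedure changes, and the hold rule stays as it is.

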### 3.15.3 Vital Sign Measurements

Vital signs will include systolic blood pressure (mmHg), diastolic blood pressure (mmHg), respiratory rate (breaths/min), heart rate (beats/min), weight (kg), BMI ( $\text{kg}/\text{m}^2$ ), and oral temperature ( $^{\circ}\text{C}$ ). The incidence rate of subjects with treatment-emergent vital sign changes at any post-baseline visit will be summarized. Specific criteria for the classification of treatment emergent are documented below. Vital sign observed and change from baseline will be summarized by treatment over scheduled visits.

Criteria for treatment-emergent changes in vital signs parameters are defined as follows.

Heart Rate:

- Low:  $< 50$  beats/min,  $> 30$  beats/min decrease from baseline
- High:  $>120$  beats/min,  $>30$  beats/min increase from baseline

Systolic Blood Pressure:

- High: > 150 mmHg, > 200 mmHg

Diastolic Blood Pressure:

- High: > 100 mmHg, > 110 mmHg

Respiratory Rate:

- Low: < 8 breaths/min
- High: >40 breaths/min

Weight

- > 5% decrease from baseline
- > 5% increase from baseline

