3.2 Subject Exclusion Criteria

Subjects will not be eligible to participate in the study if they meet any of the following criteria:

1. Clinical evidence of a lower respiratory tract infection, as determined by the Investigator.
2. Anticipated need for hospitalization or emergency room care within 24 hours of Screening.
3. Receipt of systemic antiviral, antibacterial, antifungal, or antimycobacterial therapy within 7 days of Screening and for the duration of the study.
4. Awareness of concomitant respiratory infections that are viral (other than RSV), bacterial, or fungal, including systemic bacterial or fungal infections, within 7 days of Screening.
5. Severe acute respiratory syndrome coronavirus 2 (SARS-CoV-2) positive within 28 days of Screening or at Screening following signature of full ICF.
6. Frailty scale score ≥ 4 at Screening.
7. History of chronic liver disease (eg, hemochromatosis, Wilson's disease, alpha-1 antitrypsin deficiency, autoimmune hepatitis, nonalcoholic steatohepatitis, and/or alcoholic liver disease); a history of biliary disease (eg, primary sclerosing cholangitis, cholecystitis, choledocholithiasis); or a history of portal hypertension. A diagnosis of hepatic steatosis (fatty liver) is not exclusionary.
8. Heart disease: any congenital heart disease, acute or chronic heart failure, ischemic heart disease, congenital long QT syndrome, or any clinical manifestation resulting in QT interval prolongation. Note: Subjects with controlled hypertension without cardiac compromise will be allowed to enroll. See exclusion criterion #18 for prohibited medications.
9. Neurological and neurodevelopmental disorders (including disorders of the brain, spinal cord, peripheral nerve, and muscle, eg, cerebral palsy, epilepsy [seizure disorders], stroke, muscular dystrophy, or spinal cord injury). Note: Minor neurological disorders (eg, past concussions, headaches, migraine) are allowed.
10. Malignant tumor or history of malignancy that may interfere with the aims of the study or a subject completing the study.
11. Prior receipt or the subject is waiting to receive a bone marrow, stem cell, or solid organ transplantation.
12. Diagnosis of cystic fibrosis.
13. Known positive human immunodeficiency virus, active hepatitis A virus infection, chronic hepatitis B virus infection, and/or current or treated hepatitis C virus infection.

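### The SAP's blood-pressure and respiratory-rate criteria for treatment-emergent changes have no baseline condition, so a value already beyond the limit before dosing can be counted as emergent

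*SAP*

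**What the plan says.** SAP 3.15.3 sets out the output: "The incidence rate of subjects with treatment-emergent vital sign changes at any post-baseline visit will be summarized". It then says where the rule is to be found: "Specific criteria for the classification of treatment emergent are documented below". The list that follows, introduced by "Criteria for treatment-emergent changes in vital signs parameters are defined as follows", is thus the operative definition. Its entries are of three kinds.

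- **Absolute only.** Systolic pressure is "High: > 150 mmHg, > 200 mmHg", diastolic pressure is "High: > 100 mmHg, > 110 mmHg", and respiratory rate is "Low: < 8 breaths/min" with a high limit of 40. None mentions baseline.
- **Mixed.** Each heart-rate line gives an absolute limit (below 50, above 120 beats/min), a comma, and a change of more than 30 beats/min from baseline. The SAP does not say whether the comma means *and* or *or*.
- **Relative only.** Weight is a change of more than 5% from baseline.

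Protocol 11.7.4 leaves the criteria to the SAP and adds no baseline condition. SAP 3.1 defines which value is the baseline but does not make this rule depend on it.

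For laboratory values, SAP 3.15.2 does build baseline in: "Treatment-emergent high is defined as a change from a result less than or equal to the high limit at baseline". SAP 3.15.1 counts an adverse event as treatment-emergent only if it occurs or worsens once dosing has begun.

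**The concern.** The same term has two meanings within one safety section. For laboratory values and adverse events, treatment-emergent means new or worse. For blood pressure and respiratory rate, as listed, it means present at any later visit, whatever came before. A programmer following the list would count subjects whose abnormality predates the drug.

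Such subjects can be enrolled. Protocol 3.2 states that "Subjects with controlled hypertension without cardiac compromise will be allowed to enroll", and no eligibility criterion sets a numeric blood-pressure limit. Subjects may be up to 75 years old with a body mass index up to 40 kg/m².

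At stake is how a small descriptive safety table reads. With about 35 subjects per arm, a few pre-existing elevations can form a visible part of a rate that readers will take as emerging on treatment.

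**Working it through.** The plan states no figure for this rule, so there is none to reproduce. The check has two parts.

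**1. Apply the listed criteria literally to subjects who did not get worse.**

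| Parameter | Baseline → later value | Counted as written? |
|---|---|---|
| Systolic pressure | 160 → 160 mmHg | Yes |
| Systolic pressure | 165 → 155 mmHg (improved) | Yes |
| Diastolic pressure | 104 → 104 mmHg | Yes |
| Respiratory rate | 42 → 42 breaths/min | Yes |
| Heart rate, comma read as *or* | 125 → 125, or 48 → 48 beats/min | Yes |
| Heart rate, comma read as *and* | 125 → 125, or 48 → 48 beats/min | No |
| Weight | 90 → 90 kg | No |

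On the heart-rate comma: in the systolic line, any value above 200 is also above 150, so reading that comma as *and* would make the first figure redundant. There it must separate two tiers. This suggests, without settling it, that the heart-rate limits also stand alone.

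**2. Size, for systolic pressure above 150 mmHg.**

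Input from the documents: about 35 subjects per arm (SAP 3.4). Assumptions, because the documents give neither figure: a share p of subjects starts above 150 mmHg, taken as 5–10%, and a share s of those is above it again at a later visit, taken as 50–100%. The Schedule of Assessments has only two scheduled later visits for vital signs, Day 5 and Day 14.

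Expected mislabelled subjects per arm = 35 × p × s.

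- Low end: 35 × 0.05 × 0.50 = 0.875, about 0.9
- Middle: 35 × 0.05 × 1.00 = 35 × 0.10 × 0.50 = 1.75
- High end: 35 × 0.10 × 1.00 = 3.5

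Each such subject moves an arm's rate by 1/35 = 2.9 percentage points.

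Chance of at least one in an arm = 1 − (1 − ps)^35. This is 0.59 at ps = 0.025, 0.83 at 0.05 and 0.97 at 0.10.

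Chance that the two arms differ by two or more such subjects (2/35 = 5.7 points), treating the arms as independent binomials of size 35 with the same ps: 0.23 at ps = 0.025, 0.39 at 0.05 and 0.54 at 0.10.

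With a condition that the criterion was not already met at baseline, none of the subjects in the table above is counted.

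**The case against.** The case for leaving the text alone has several parts.

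**Baseline is not ignored throughout.** This is correct. A reader might infer that all the vital-sign criteria disregard baseline. Weight is wholly relative to baseline, and heart rate has a change element that would protect it entirely if the comma means *and*.

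**High baseline pressure need not be common.** A reader might infer from the hypertension note that values above 150 mmHg before dosing are to be expected. The note admits only controlled hypertension, and inclusion criterion 5 requires medical stability judged partly on vital signs. With no numeric limit such values are possible, but the documents do not support saying more. A respiratory rate below 8 or above 40 at entry is improbable in ambulatory, stable subjects, so the defect there is mainly one of principle.

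**The consequence is contained.** The safety analyses are mainly descriptive. The same section summarises observed values and change from baseline, all subject data are listed individually, and randomization leaves only chance imbalance. This stands and limits the importance of the point. It does not remove it, because group means do not show which counted subjects were abnormal before dosing.

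**A shift was probably intended.** The wording of the section points that way, and the table shells are in a separate document. But the section says its criteria are those listed, and no listed criterion for these three parameters requires a shift.

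**A simple baseline exclusion has a cost.** If a criterion counted only when unmet at baseline or when a higher tier is newly crossed, a rise from 152 to 198 mmHg systolic, or from 101 to 109 mmHg diastolic, would drop out. The present rule counts both. This objection is sound, and the fix must deal with it.

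**Conclusion.** The point holds for systolic and diastolic pressure, in principle for respiratory rate, and for the absolute heart-rate limits only if the comma means *or*. Weight is not affected. As written, the rule classes unchanged and improved subjects as treatment-emergent, and no other section of either document corrects this.

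Under the two assumptions stated (5–10% above 150 mmHg at baseline, 50–100% of them still above it later), about 0.9–3.5 subjects per arm would be mislabelled for systolic pressure, or 2.5–10 percentage points of the arm's rate (0.875/35 to 3.5/35). If few subjects enter above the limit, the effect is correspondingly small.

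A reader might go further and infer that the table could hide a real safety signal or create a false one. The documents do not support that. The table feeds no test, no efficacy result and no stopping rule (Protocol 10.1 uses graded adverse events and laboratory abnormalities), and the change-from-baseline summaries and listings stand beside it. What remains is an inflated, mislabelled descriptive incidence that chance may leave uneven between arms. This is a minor definitional repair, worth making because it is cheap.

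**What to change.** In SAP 3.15.3, state that a criterion counts as treatment-emergent only if it was not met at baseline, or if the value worsened from baseline beyond it. Define worsening as a higher tier newly crossed or a pre-specified increase within the tier, so that deterioration in subjects already above the first cut-off is kept. State also whether the heart-rate comma means *and* or *or*.

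Alternatively, keep the cut-offs as they are, relabel the table as post-baseline values meeting a threshold, and show it by baseline status. This removes the mislabelling with no loss of sensitivity.

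The first option costs one sentence and one programming condition. Baseline vital signs are already taken at Screening on Day 1, so no new data are needed. The drawback is a small loss of sensitivity if within-tier worsening is not retained. Protocol 11.1 allows changes in the SAP only before unblinding, so the edit should be made by then.

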11.7.4 Vital Sign Measurements

The incidence rate of subjects with treatment-emergent vital sign changes at any post-Baseline visit will be summarized. Specific criteria for the classification of treatment emergent will be

documented in the SAP. Vital sign observed, change, and percentage change will be summarized by treatment over visits.

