#### 2.2.2 Secondary Endpoints

- AUC from Day 1 through Day 14 for RSV RNA viral load measured in nasopharyngeal swab samples by quantitative reverse transcription polymerase chain reaction (RT-qPCR)

- Percentage of subjects with RSV RNA viral load below the limit of detection on Days 3, 5, 9 and 14 respectively
- Plasma PK concentrations of EDP-938 and its major metabolites (EP-024636, EP-024594, and EP-024595) on Days 1, 3 and 5
- Safety endpoints include, but are not limited to, AEs, vital sign measurements, pulse oximetry measurements, and clinical laboratory test results (including chemistry, hematology, and urinalysis)
- Time to RSV RNA viral load below the limit of detection
- RSV RNA viral load and change from baseline over time

[REDACTED]

[REDACTED]

[REDACTED]

[REDACTED]

[REDACTED]

[REDACTED]

[REDACTED]

[REDACTED]

[REDACTED]

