### 3.15 Safety Analyses

Statistical methods for the safety analyses will be primarily descriptive in nature. The SAF will be used for all analyses, unless stated otherwise.

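### SAP 3.15.3 gives systolic and diastolic pressure high limits only, so the treatment-emergent vital-sign table cannot count low readings (minor, one descriptive table)

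*SAP*

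**What the plan says.** Protocol 11.7.4 plans an incidence summary of treatment-emergent vital-sign changes and sets no limits of its own. It says "Specific criteria for the classification of treatment emergent will be" given in the SAP.

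SAP 3.15.3 takes this up: "The incidence rate of subjects with treatment-emergent vital sign changes at any post-baseline visit will be summarized". It adds: "Specific criteria for the classification of treatment emergent are documented below". The list that follows is complete in itself and refers to no other source. For systolic pressure it reads "High: > 150 mmHg, > 200 mmHg" and for diastolic pressure "High: > 100 mmHg, > 110 mmHg". Heart rate and respiratory rate each have a low line and a high line, and weight has a decrease line and an increase line.

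The same section also plans by-visit output: "Vital sign observed and change from baseline will be summarized by treatment over scheduled visits". SAP 3.15 describes the safety analyses as a whole: "Statistical methods for the safety analyses will be primarily descriptive in nature".

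**The concern.** Blood pressure is the only sign with criteria that is judged in one direction. The laboratory section (SAP 3.15.2) also defines both treatment-emergent high and treatment-emergent low for continuous tests. No reason is given for treating blood pressure differently.

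The consequence is specific. In the one vital-sign table that counts subjects across visits, a subject with low pressure after dosing appears as having no blood-pressure change.

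Vital signs are a named safety endpoint in SAP 2.2.2: "Safety endpoints include, but are not limited to, AEs, vital sign measurements, pulse oximetry measurements, and clinical laboratory test results". The documents give modest reasons to want the count in both directions:

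- Protocol 3.2 (exclusion 8) admits subjects whose hypertension is controlled.
- Protocol 1.5 records somewhat more dizziness on EDP-938 than on placebo in the Phase 2a study, although the cases were few and mild and cleared.
- The Schedule of Assessments has an ECG at Screening only, and pulse oximetry only for subjects with asthma or COPD. For everyone else, blood pressure and heart rate are the only objective cardiovascular measurements scheduled after dosing.

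Timing matters too. Protocol 11.1 allows SAP changes only until unblinding, and a low limit chosen after that would be post hoc.

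**Working it through.** The plan states no figure to reproduce, so the check is a reading of the criteria list and then of the other planned outputs.

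**Step 1: threshold values in SAP 3.15.3, by direction.**

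| Sign | Downward | Upward |
|---|---|---|
| Heart rate | 2 (<50 beats/min; fall >30) | 2 (>120 beats/min; rise >30) |
| Systolic pressure | 0 | 2 (>150; >200 mmHg) |
| Diastolic pressure | 0 | 2 (>100; >110 mmHg) |
| Respiratory rate | 1 (<8 breaths/min) | 1 (>40 breaths/min) |
| Weight | 1 (fall >5%) | 1 (rise >5%) |
| Total | 2+0+0+1+1 = 4 | 2+2+2+1+1 = 8 |

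Total: 4 + 8 = 12 values. Blood pressure has 4, of which 0 point downward. The two tiers for each pressure are nested, so 8 against 4 is not a measure of size. What counts is the zero.

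**Step 2: is a low limit given elsewhere, or lost from the text?** Neither document contains a low blood-pressure limit or a fall-from-baseline criterion for blood pressure. There is no redaction mark at those lines, and the low lines for heart rate and respiratory rate are intact, so loss of text is unlikely.

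**Step 3: what the criteria flag.** The pressure limits are absolute values with no baseline element. As written they flag high readings, not rises. A systolic reading of 150 mmHg or less, or a diastolic reading of 100 mmHg or less, meets no criterion however low it is.

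**Step 4: what the other outputs supply.**

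- *By-visit summaries* (SAP 3.15.3, with the statistics named in SAP 3.1). The minimum shows whether anyone was below a given limit at a visit. If no minimum is below it, the count is zero. If one is, the summary does not say how many subjects were low or whether the Day 5 and Day 14 cases are the same person. It also does not say whether the low value was a fall for that subject, because observed values and changes are summarised separately.
- *Adverse event tables* (SAP 3.15.1). These count a low reading only if it was recorded as an adverse event, which rests largely on the investigator's judgement (Protocol 9.1.2).
- *Listings* (SAP 3.1). Every subject's data are listed by site, subject and time, with the treatment group shown. About 70 subjects with two scheduled post-baseline visits give 70 × 2 = 140 sets of readings, few enough to count by hand.

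**Step 5: weight of one case.** With 35 subjects planned per arm, one subject is 1/35 = 2.9%.

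**The case against.** The strongest reply is that nothing in the plan is broken. The protocol left the criteria to the SAP, the SAP supplied them, and neither document promises two-sided limits for every sign. The SAP is selective elsewhere: temperature and BMI have no criteria, and most laboratory tests have extra high tiers but a single low one. Hypotension judged to be an adverse event would be graded and tabulated by arm, and a Grade 4 event on EDP-938 would trigger the stopping rules in Protocol 10.1. The listings already hold every reading.

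The yield would also be small. Readings are taken lying down after at least five minutes (Protocol 8.3.1), and Day 14 comes 9 days after the last dose. The Day 5 visit is meant to fall near the usual dosing time, so that reading may be close to trough. This last point is an inference, because the timing of vital signs relative to dose is not stated.

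Most of this stands. There is no conflict between protocol and SAP, the yield is limited, and the listings would allow the count. It does not explain why the one table designed to count subjects across visits can count them in only one direction for blood pressure.

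A reader might infer more than the documents support:

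- *That low pressure would go unseen.* It would not: by-visit minima, changes from baseline, adverse event tables and listings all remain.
- *That EDP-938 is suspected of lowering blood pressure.* Nothing visible says so. Protocol 1.3.3 reports nothing of concern from safety pharmacology (its detail is redacted), and dizziness is listed beside headache and diarrhea, all mild.

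**Conclusion.** The point holds as a minor one. The treatment-emergent vital-sign table can flag high blood-pressure readings and never low ones, so a hypotensive subject is not counted in it. The information is untabulated rather than unavailable. The efficacy analyses, adverse event tables and stopping rules are unaffected.

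No event rate is claimed. If every by-visit minimum is above the chosen low limit, the missing rows would be zero and nothing is lost. If any is below, each affected subject is 2.9% of a planned arm, and no planned vital-sign table gives the total per arm.

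The conclusion assumes that the list in SAP 3.15.3 is the whole set of criteria, as its wording indicates. The separate table shells are not among the documents.

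**What to change.** Before unblinding, add one low systolic and one low diastolic criterion to SAP 3.15.3, using the sponsor's standard limits. As an illustration only, and an assumption not taken from the documents: systolic <90 mmHg with a fall of at least 20 mmHg from baseline, and diastolic <50 mmHg with a fall of at least 15 mmHg.

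The data are already collected at Screening, Day 5 and Day 14, so no new procedure is needed. The cost is two table rows that may be empty.

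No temperature row is needed. Fever symptoms are already a twice-daily diary item, and a fever count would be confounded by the infection itself and by permitted acetaminophen.
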